5.2.2. Associated with phlebotomy

Localised bruising and discomfort can occur at the site of venepuncture. Infrequently fainting may occur. These will not be documented as AEs if they occur. Blood volumes collected will adhere to EC directive 2001/20/EC for paediatric blood volume sampling which states that ‘per individual, the trial-related blood loss (including any losses in the manoeuvre) should not exceed 3 % of the total blood volume during a period of four weeks and should not exceed 1% at any single time’. Based on these calculations, we will take 16ml per sampling timepoint from participants aged 12-16 years on each visit for immunology bloods. Some participants will turn 17 during the trial and become eligible for blood donation; they will be asked to refrain from this for the duration of their trial involvement.

5.2.3. Associated with saliva sampling

Participants may find the saliva collection process unsavoury as it involves drooling and spitting. This will be an optional element of the study.

5.2.4. Associated with nasal fluid sampling

Localised discomfort can occur in the nostril. Infrequently, this can result in a small amount of epistaxis, which can be controlled with pressure to the affected area. This will be an optional element of the study.

5.2.5. Allergic reactions

Allergic reactions from mild to severe may occur in response to any constituent of a medicinal product’s preparation. Anaphylaxis is known to occur in approximately 2.5 to 4.7 per million recipients of mRNA COVID-19 vaccines,(20) and more generally in around 1 in 1,000,000 doses of all vaccines, but can occur in response to any vaccine or medication.(21)

5.2.6. Behaviour change

Participants might feel they can modify their COVID-19 risk behaviours on the assumption that they are protected once vaccinated. Participants will be counselled that they should continue to follow all up to date government advice in relation to COVID-19 precautions during the trial.

5.2.7. Specific risks from vaccines

Please refer to section 11.8 for full details.

5.2.8. Receiving a sub-optimal vaccine schedule

It is possible that one or more of the combinations of vaccine schedule used in this trial is, on analysis found to generate a humoral or cellular immune response lower than that of the licensed homologous BNT162b2 schedule. If this were to be the case, advice would be sought from the DSMB and TSC, who might recommend further doses of vaccine to any disadvantaged participant, if possible (either via the study or through the NHS).

5.2.9. Unwanted media attention

Trial participants can be subjected to unwanted attention from the media. They will therefore be provided with access to a document outlining some suggested media guidance.

6. OBJECTIVES AND OUTCOME MEASURES

	Objectives	Outcome Measures	Timepoint(s)
Primary	To evaluate the reactogenicity of heterologous boost at least 8 weeks following BNT162B2 prime vaccine administered to adolescents.	Solicited reactions systemic	7 days after boost immunisation
Secondary	To assess safety of heterologous boost COVID-19 vaccines	Serious adverse events Adverse events of special interest	Throughout the study
	To characterise immunogenicity of heterologous & homologous boost schedules	Anti-spike immunoglobulins	D0*, 56, post prime D 14, 28, 132, 236 post boost
		Anti-nucleocapsid immunoglobulins	D0*, 56 post prime D132, 236 post boost
		Cellular immune responses by ELISpot	D0*, 56 post prime

			D 14, 132, 236 post boost
	To assess reactogenicity and safety of heterologous and homologous boost schedules of COVID-19 vaccines	Solicited local reactions	7 days after prime* and boost immunisation
		Unsolicited reactions	28 days after prime* and boost immunisation
	To evaluate immunogenicity, safety & reactogenicity of COVID-19 vaccines in participants seropositive for SARS-CoV-2 nucleocapsid IgG at enrolment, compared with seronegative	Immunogenicity, safety & reactogenicity endpoints as outlined above	Timepoints as outlined above
Exploratory	To assess incidence of SARS-CoV-2 infection in participants receiving heterologous & homologous prime/boost schedules	Self-reported SARS-CoV-2 infection, from community testing	Throughout the study
	To further characterise the blood antibody response	Neutralizing and Functional antibody assays	D0*, 56 post prime D 14, 28, 132, 236 post boost
	To characterise and compare the mucosal immune response to immunisation with homologous and heterologous COVID-19 vaccines using nasal fluid (collected using SAM-strips) and saliva samples	IgA & IgG ELISA and exploratory immunological assays	D0*, 56 post prime D14 post boost
	To determine normal ranges of markers of cardiac muscle damage in adolescents, and to assess change post-immunisation	High sensitivity troponin and N-terminal pro B-type natriuretic peptide (NT-proBNP)	D0*, 56 post prime D14, 28 post boost

* Only for participants receiving prime vaccination in the study

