9.6. Visits

The study visits and procedures will be undertaken by one of the clinical trials team. The procedures to be included in each visit are documented in the schedule of attendances (Each visit is assigned a time-point and a window period, within which the visit will be conducted. If a participant cannot attend a visit, where possible, this will be re-arranged to an in-person visit within the time window. A telephone visit may be conducted instead of the in-person visit to ascertain as much relevant information as possible if the participant is unable to attend a visit in person because of quarantine or self-isolation restrictions and the participant will be out of window if the visit is postponed.

Participants may enrol in the study either before receiving a COVID-19 vaccine (study-prime) or after receiving a first dose of Pfizer-BioNTech vaccine in the community (community-prime). The details of the D0 and D56 visits will differ for these two scenarios, as described below.

9.6.1. Visits for participants receiving their first dose of COVID-19 vaccine in the study

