9.6.1.1.4. Vaccination at D0

Participants will be considered enrolled to the trial at the point of receipt of the first vaccine administered by the study team. All vaccines will be administered intramuscularly according to specific SOPs. The participant will stay in the trial site for observation for at least 15 minutes, in case of immediate adverse events. Participants will be issued with an NHS COVID-19 vaccination record card at the first immunisation with entry of “BNT162b2” and batch number. This will be updated at the second immunisation, but boost vaccine type or batch number will not be added as this would unblind participants; instead, “COVID-19 vaccine”, “Com-COV3 Trial” will be added. We will correspond with holders of the participant’s medical information records (e.g. GPs) to enable updating of these records.

9.6.1.1.5. eDiary

Participants/parents/guardians will be given an oral thermometer, tape measure and diary (electronic, but for those who are unable to use an electronic diary, a paper version will be made available), with instructions on use. All participants will be given the emergency 24-hour telephone number to contact the on-call study physician if needed. Participants/parents/guardians will be instructed on how to self-assess the severity of the solicited and unsolicited AEs they are entering in the diaries. There will also be space in the diary to self-document unsolicited AEs, and whether medication was taken to relieve the symptoms. It will also log any serious medical illnesses or hospital visits which may have occurred over the entire course of the study and any diagnosis of SARS-CoV-2 infection. Given the potential for physical exercise to raise troponin and NT-proBNP independently of myocardial inflammation, there will be a space in the diary to record episodes of strenuous physical activity (“defined as anything that makes you feel really out of breath”) in the period between the booster vaccine and the D70 visit. Participants/parents/guardians will be asked to report on solicited AEs for 7 days from prime and boost dose (and longer if symptoms persist at day 7, until resolution or stabilisation of symptoms) and unsolicited AEs for 28 days. The Diary will collect information on the timing and severity of the following solicited AEs:

Table 1 Solicited AEs collected on post vaccination diary cards

Com-COV3 Protocol

©Copyright: The University of Oxford

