12.4. Interim analyses

The analysis on the primary endpoint of reactogenicity, i.e. solicited AEs will be carried out once the 7-day e-diary data become available. The analysis on the secondary endpoint of immunogenicity will be carried out when the D70 immunogenicity data, i.e. 14 days post boost, become available. The interim analyses will provide evidence for policy making as to the recommendation on the second dose of COVID-19 vaccine among adolescents. The interim analyses will be carried out once the data is cleaned and the Study Analysis Plan is signed off. There will be no stopping rule for this interim analysis and the analysis will not affect the continuation of the trial.

After further discussion with Joint Committee on Vaccination and Immunisation (JCVI), the study team decided to carry out another interim analysis in December 2021. In this analysis, we will review the sero-status pre-boost as well as all the available immunogenicity data. These data will be shared with JCVI only to support decision making on boost dose among people aged 12-17. This interim analysis will be descriptive.

On 29th November 2021, the JCIV recommended that all 12 to 15 year-olds should be offered a second dose of BNT162b2 vaccine before reviewing the planned interim analysis in December 2021. The study design was amended to focus on immune response to full dose and one third dose of BNT162b2. The planned analysis in December will still be conducted and results will be

presented to JCVI to update their recommendation. The study's recruitment and sample size will then be reviewed on the basis of this analysis after discussing with JCIV, TSC and DSMB.

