25. APPENDIX C: BLOOD SAMPLING

Study timeline	D0	D56	D14 post boost	D28 post boost	D132 post boost	D236 post boost
COVID-19 vaccination	X	X				
Secondary endpoints	Anti-spike IgG* Anti-nucleocapsid IgG* ELIspot* Troponin & NT-proBNP*	Anti-spike IgG Anti-nucleocapsid IgG ELIspot Troponin & NT-proBNP	Anti-spike IgG ELIspot Troponin & NT-proBNP	Anti-spike IgG PBMC for storage Troponin & NT-proBNP	Anti-spike IgG Anti-nucleocapsid IgG ELIspot	Anti-spike IgG Anti-nucleocapsid IgG ELIspot
Total volume blood per visit	16	16	16	16	16	16
Total volume by end of study						96 ml

* Procedures performed only if prime dose administered in the study

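### Serostatus taken at enrolment means before the prime for study-primed and at the boost for community-primed participants, so the same infection between doses gets opposite labels in the post-boost serostatus comparison

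*Protocol*

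**What the plan says.** The secondary objective in protocol section 6, repeated in the synopsis (section 3), is: "To evaluate immunogenicity, safety & reactogenicity of COVID-19 vaccines in participants seropositive for SARS-CoV-2 nucleocapsid IgG at enrolment, compared with seronegative". It applies to all the immunogenicity, safety and reactogenicity endpoints and timepoints listed above it in the table.

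Section 9.6.1.1.4 defines enrolment: "Participants will be considered enrolled to the trial at the point of receipt of the first vaccine administered by the study team". The synopsis agrees. Section 9.6 allows two routes: "Participants may enrol in the study either before receiving a COVID-19 vaccine (study-prime) or after receiving a first dose of Pfizer-BioNTech vaccine" in the community.

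The anti-nucleocapsid row of the section 6 table lists D0 and D56 before the boost. The D0 entry carries an asterisk, explained as "Only for participants receiving prime vaccination in the study". Appendix C marks the D0 column in the same way ("Anti-spike IgG* Anti-nucleocapsid IgG* ELIspot* Troponin & NT-proBNP" with a footnote limiting these assays to participants primed in the study) and lists D56 anti-nucleocapsid IgG without that limit. Section 9.6.2 places the blood sampling of community-primed participants at the D56 visit.

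Pre-boost serostatus is mentioned once, for the descriptive December 2021 interim analysis in section 12.4: "we will review the sero-status pre-boost as well as all the available immunogenicity data".

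**The concern.** One word, enrolment, points to two different times relative to vaccination. For study-primed participants it comes before any dose and at least 56 days before the boost. For community-primed participants it is the boost visit itself.

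The protocol expects infections in between. Section 7.4 lets newly infected participants continue, and section 8.3.1 defers vaccination only when infection was first confirmed less than 4 weeks previously. Under the rule as written, a study-primed participant infected in that interval stays in the seronegative group for every post-boost endpoint, although the D56 sample may already show otherwise.

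At stake is the post-boost comparison of seropositive with seronegative participants, and the seronegative GMC as a description of infection-naive adolescents. Section 7.3 adds weight: after 29 November 2021 only study-primed participants are randomised, so the affected cohort is the one still being randomised.

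**Working it through.** **Step 1. The two routes side by side.** Take two adolescents, both uninfected at the prime, both infected between prime and boost, both with detectable anti-nucleocapsid IgG at D56.

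| | Study-primed | Community-primed |
|---|---|---|
| Enrolment (sections 3, 9.6.1.1.4) | D0, the prime | D56, the boost |
| Prime-to-boost window (Appendix A) | 56-70 days | 56 days or more |
| Sample that fixes serostatus | D0 | D56 |
| Label for post-boost endpoints | seronegative | seropositive |

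This step needs no assumption beyond the protocol's own definitions.

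**Step 2. Is D56 a usable marker of infection?** Section 10.1.1 describes BNT162b2 as encoding spike, and every prime is BNT162b2. The prime should therefore not itself produce anti-nucleocapsid antibody.

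**Step 3. Size.** The protocol gives no infection rate and no effect of infection on the response, so both are assumed. Let

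- q = share of D0-seronegative study-primed participants infected before the boost (assumed 5-20%),
- R = true infected/uninfected ratio of post-boost GMC (assumed 2 to 4, and the same for recent and earlier infection),
- f = study-primed share of the analysed seronegative group (1 or 0.5 for illustration),
- m = f × q = misclassified share.

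The mean log response of the seronegative group rises by m × log R. Its GMC is therefore multiplied by R^m, and the observed seropositive/seronegative ratio is R^(1−m).

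| f | q | R | m | GMC factor R^m | Observed ratio |
|---|---|---|---|---|---|
| 1 | 5% | 2 | 0.05 | 1.04 | 1.93 |
| 1 | 10% | 3 | 0.10 | 1.12 | 2.69 |
| 1 | 20% | 4 | 0.20 | 1.32 | 3.03 |
| 0.5 | 5% | 2 | 0.025 | 1.02 | 1.97 |
| 0.5 | 20% | 4 | 0.10 | 1.15 | 3.48 |

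**Step 4. Precision.** The nearest figures in the protocol are the minimum detectable geometric mean ratios (GMRs) in section 12.1: 1.57, 1.75 and 1.96 for log10 SD 0.4, 0.5 and 0.6, with 90 per arm, 90% power and two-sided 0.05. The formula 10^(SD × √(2/90) × (1.960 + 1.282)) gives 1.56, 1.74 and 1.95, and the noncentral t version gives 1.56, 1.75 and 1.96. The table reproduces to within 0.01 and is not in dispute.

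A mixed group adds log10 variance q(1−q) × (log10 R)². In the worst corner assumed here this is 0.20 × 0.80 × 0.6021² = 0.058. With SD 0.4 the SD becomes √(0.16 + 0.058) = 0.47, and the detectable GMR moves from 1.56 to 1.68. This is illustrative only: section 12.1 gives whole-arm SDs and numbers, and a seronegative subgroup would be smaller.

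**The case against.** **The SAP may settle it.** Section 12.2 is a summary, and subgroup definitions are often left to the SAP, which is not shown. This would answer a complaint about missing detail. Here, however, the protocol objective itself fixes the time of classification. A SAP using pre-boost status for study-primed participants would depart from that wording, so the two should be aligned.

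**Pre-prime status is right for some endpoints.** This stands. The objective covers D56 immunogenicity and, for study-primed participants, local reactions over 7 days and unsolicited reactions over 28 days after the prime. For those, D0 is the proper classifier. The defect is confined to post-boost endpoints.

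**After 29 November 2021 the definition is uniform.** Only study-primed participants are then randomised, so no new inconsistency between cohorts arises among them. The misclassification of infections between D0 and D56 remains.

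**Two stronger readings are tempting and are not supported.**

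- A reader might infer that everyone infected between doses is analysed as seronegative. Community-primed participants are sampled at the boost visit, so their infections are captured once antibody is detectable.
- A reader might infer that the comparison of one-third with full dose is biased. Section 12.2 does not restrict that comparison to seronegatives. Randomisation takes place at the second dose (sections 7.3 and 9.4), so earlier infections are balanced between arms in expectation. At most, precision suffers.

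Nor do the documents show that stratification used D0 status. It uses baseline status where available, without tying baseline to a visit.

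**Conclusion.** The point holds for study-primed participants who are seronegative at D0 and infected before the boost, and for post-boost endpoints only. The opposite labelling by priming route follows directly from the protocol's definitions.

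The size cannot be derived from the protocol. Under the stated assumptions the seronegative GMC is inflated, and the serostatus ratio reduced, by a factor of 1.04 to 1.32 in a wholly study-primed group. With half the group community-primed, the factor is 1.02 to 1.15.

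The consequence is dilution of one secondary, non-randomised contrast. Serostatus does not define the primary endpoint. This is a modest defect, worth correcting because the remedy uses data already planned.

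**What to change.** In sections 3 and 6, replace the single reference to enrolment with a rule for each set of endpoints:

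- for all post-boost endpoints, serostatus is defined by the pre-boost (D56) anti-nucleocapsid sample in both cohorts;
- for post-prime endpoints in study-primed participants, serostatus is defined by the D0 sample;
- participants who seroconvert between D0 and D56 are reported separately.

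Use the same rule in the SAP, before the serostatus analysis is run. Simply substituting D56 for enrolment throughout would not do, because it would classify reactions to the prime by a result obtained 8 weeks later.

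The cost is a wording change. No new sample or assay is needed, since D56 anti-nucleocapsid IgG is already scheduled for everyone. Infections without detectable anti-nucleocapsid antibody at D56 would still be missed, and the report should say so.

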7.4. Participants testing COVID-19 positive

Participants who acquire new infection with SARS-CoV-2 (as determined by SARS-CoV-2 antigen or PCR tests) will be asked to record this in their electronic/paper diary, and may continue in the study.

The UKHSA recently recommended increasing the interval between COVID-19 infection and vaccination from 4 weeks to 12 weeks in healthy 12 to 17 year olds. This is in part because young people are likely to have high levels of protection for at least 3 months after COVID-19 infection, meaning an earlier vaccine boost might not be necessary. It is also possible, though not confirmed, that a longer interval between infection and vaccination might reduce further the very small existing risk of myocarditis. The recommendation adopts a highly precautionary approach. However, 12 to 17 year olds at “high risk” and all adults are still advised to wait 4 weeks between infection and vaccination. On the advice of our independent Trial Steering Committee, we will still be offering a second dose of vaccination from 4 weeks after the first positive COVID-19 test confirming infection. This is in line with the recommendation for ‘high-risk’ 12 to 17 year olds. This is to allow as many adolescents as possible to take part in this study, and to enable us to provide results as quickly as possible to the JCVI.

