9.5. Blinding and code-breaking

The study will be single-blind. Staff involved in study delivery will be aware of which vaccine the participant is receiving (arm allocation); the participant will remain blinded to their boost vaccine allocation up until the day 84 visit, at which point participants will be advised of their immunisation arm. Vaccines will be prepared out of sight of the participant and the blind will be maintained by applying a masking tape over the vaccine syringe. Laboratory staff will also be blinded to the vaccine schedule received.

If the clinical condition of a participant necessitates unblinding of the participant prior to the day 84 visit, this will be undertaken according to a trial specific working instruction and group allocation sent to the attending physician. This will be done if unblinding is thought to be relevant and likely to change clinical management.

In order not to disadvantage participants in a rapidly changing landscape of rules affecting national and international travel as well as event attendance, we will make every effort to liaise with appropriate parties to ensure participants' vaccination status is recorded in the most suitable manner.

As of the 11th June 2021, the Department of Health and Social Care has confirmed that for any future domestic certification of vaccination status, clinical trial participants will not be disadvantaged, and will be offered an "immunised" status regardless of the licencing status or vaccine schedule received. This status would be available to trial participants while blinded, and also after unblinding even if they have received an unlicensed vaccine schedule.

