13.2. Data Recording

All study data including participant diary will be recorded directly into an EDC system (REDCap) or onto a paper source document for later entry into EDC if direct entry is not available. This includes safety, laboratory and outcome data. Any additional information that needs recording, but is not relevant for the eCRF (e.g signed consent forms) will be recorded on separate paper source documents. All documents will be stored safely and securely in confidential conditions. The EDC online data is stored on University of Oxford servers.

All participant reported adverse event data (both solicited & unsolicited) will be entered onto electronic diary cards (e-diaries) for a maximum of 28 days following administration of the IMP. The e-diary provides a full audit trail of edits and will be reviewed at time-points as indicated in the schedule of events. Any adverse event continuing beyond the period of the diary will be copied into the eCRF as required for safety review.

The participants will be identified by a unique trial specific number and code in any database. The name and any other identifying detail will NOT be included in any trial data electronic file, with the exception of the electronic diaries, for which consent will be obtained to store the participant email address for quality control purposes. Only site research staff and sponsor data managers have access to view the email address.

The EDC system (CRF data) uses a relational database (MySQL/ PostgreSQL) via a secure web interface with data checks applied during data entry to ensure data quality. The database includes a complete suite of features which are compliant with GCP, EU and UK regulations and

Sponsor security policies, including a full audit trail, user-based privileges, and integration with the institutional LDAP server. The MySQL and PostgreSQL database and the webserver will both be housed on secure servers maintained by the University of Oxford IT personnel. The servers are in a physically secure location in Europe. Backups will be stored in accordance with the IT department schedule of daily, weekly, and monthly retained for one month, three months, and six months, respectively. The IT servers provide a stable, secure, well-maintained, and high-capacity data storage environment. REDCap is a widely-used, powerful, reliable, well-supported system. Access to the study's database will be restricted to members of the study team by username and password.

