23. APPENDIX A: SCHEDULE OF PROCEDURES

Study timeline	Screening	D0	D56	D14 post boost	D28 post boost	D132 post boost	D236 post boost
Study window		Within 120 days of screening	Day 56–70 post prime vaccine at D0 or Day 56 + post prime vaccination in community	Day 12-17 Post D56	Day 28-42 post D56	Day 112-152 post D56	Day 224-252 post D56
Pre - screening online consent	X*						
Informed consent	X	X					
Medical history	X	X					
Interim medical history		X	X	X	X	X	X
Physical examination (as required)	(X)	(X)	(X)	(X)	(X)	(X)	(X)
Urine test (Pregnancy) (if required)		(X)**	X				
COVID-19 vaccination		(X)**	X				

COVID-19 immunogenicity bloods		(X)**	X	X	X	X	X
Troponin and NT-proBNP blood test		(X)**	X	X	X		
Saliva and nasal fluid test (if participant consents)		(X)**	X	X			
Diary review			X	X	X		
SAE/AESI check			X	X	X	X	X

* Pre - screening online consent. Restricted to taking a limited medical history online, contacting the GP for further medical record if required and telephone screening visit(s)

**Procedures performed only if prime dose administered in the study

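### The exploratory infection objective relies on self-reported community tests, mostly after participants know their arm, while anti-N serology already scheduled and read blind is not linked to it

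*Protocol*

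**What the plan says.** The protocol's Section 6 (repeated in the Section 3 synopsis) sets this exploratory objective: "To assess incidence of SARS-CoV-2 infection in participants receiving heterologous & homologous prime/boost schedules". Its only outcome measure is "Self-reported SARS-CoV-2 infection, from community testing".

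The protocol describes these routes for capturing an infection:
- Under Section 7.4, participants with a positive antigen or PCR test "will be asked to record this in their electronic/paper diary, and may continue in the study". Section 9.6.1.1.5 also says the diary logs any SARS-CoV-2 diagnosis.
- Section 11.10 lists a positive validated test as an adverse event of special interest (AESI). Section 11.6.2 has AESIs asked about at every visit, and Appendix A shows that check through D236 post boost.
- Section 9.6.4 requests hospital notes for COVID-19 admissions.

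On blinding, Section 9.5 keeps participants "blinded to their boost vaccine allocation up until the day 84 visit, at which point participants will be advised of their immunisation arm". Staff delivering the study know the arm throughout. Laboratory staff are blinded to the schedule.

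Appendix C lists "Anti-nucleocapsid IgG" at D0 (study-primed participants only), at D56 (no such restriction), and at D132 and D236 post boost. In Section 6 these measurements stand under the secondary immunogenicity objective. Enrolment serostatus also defines a subgroup objective and, where available, a stratification factor. Nothing ties post-boost anti-N to the infection objective.

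**The concern.** Whether an infection is counted depends on whether the participant chose to test and then told the study. A participant who has been told they received a one-third dose or a different vaccine may test or report more, or less, than one told they received the full BNT162b2 dose. The protocol accepts this mechanism elsewhere: Section 17.4 excludes staff relatives because learning the allocation could affect how they complete their diaries.

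Two things are at stake. A difference in reported infection between arms could reflect testing behaviour rather than infection. Infections that nobody tested for are also lost in every arm. A measurement that does not depend on test-seeking is already in the sampling plan.

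**Working it through.** **1. Figures in the plan.** The protocol states no figure for infection incidence. Its precision table in Section 12.1 concerns systemic reactions at 90 per arm and reproduces (at 50%, 1.96 × √(0.5 × 0.5 / 90) = 10.3%). It does not bear on this objective.

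**2. Share of follow-up after unblinding.**

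Inputs:
- Day 84 is D56 + 28, so it is the D28 post-boost visit. Its window in Appendix A is "Day 28-42 post D56".
- The last visit is D236 post boost, window 224 to 252 days (Appendix A).
- Section 7.2 states about 26 weeks (182 days) for community-primed and 34 weeks (238 days) for study-primed participants.

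Formula: (last day − unblinding day) / last day.

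| Basis | Calculation | Share unblinded |
|---|---|---|
| Post boost, nominal | (236 − 28)/236 = 208/236 | 88.1% |
| Late unblinding, early last visit | (224 − 42)/224 = 182/224 | 81.3% |
| Early unblinding, late last visit | (252 − 28)/252 = 224/252 | 88.9% |
| Section 7.2 duration, community-primed | (182 − 28)/182 = 154/182 | 84.6% |
| From D0, study-primed, nominal | 208/(56 + 236) = 208/292 | 71.2% |
| Section 7.2 duration, study-primed | (238 − 84)/238 = 154/238 | 64.7% |

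It is a clear majority on every basis. The Section 7.2 durations do not fit a last visit at D236 post boost, but the conclusion does not depend on which is right.

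**3. Does any capture route avoid test-seeking?** Diary entry needs a test result. The AESI question at visits needs a validated test and disclosure, and is put by staff who know the arm. Hospital notes avoid this dependence only for admitted cases. Appendix A schedules no study swabs.

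**4. Is anti-N specific to infection here?** Section 10.1.1 describes BNT162b2 as encoding spike, and Section 10.1.2 describes NVXCoV2373 as built from spike trimers. Neither is described as containing nucleocapsid, so new anti-N after the boost points to infection. Section 9.2.1 already accepts nucleocapsid antibody as evidence of past infection.

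**5. What differential ascertainment does (assumed inputs only).** If true risk p is equal in two arms and fractions s₁ and s₂ of infections are reported, the observed ratio is p·s₂ / (p·s₁) = s₂/s₁. With assumed p = 30%:

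| s₁, s₂ | Observed risks | Ratio |
|---|---|---|
| 0.7, 0.6 | 21% v 18% | 0.86 |
| 0.8, 0.6 | 24% v 18% | 0.75 |
| 0.8, 0.5 | 24% v 15% | 0.625 |

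The ratio inverts if the arms swap. None of these inputs is in the documents; the table shows the mechanism and not an expected bias.

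**6. What serology can resolve.** Nominal intervals are 132 days (D56 to D132) and 236 − 132 = 104 days (D132 to D236). The first contains the 28 blinded days and 132 − 28 = 104 unblinded days. Anti-N is not scheduled at D14 or D28, so serology cannot separate the blinded period.

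**The case against.** **Low tier.** The objective is exploratory, its wording is to assess incidence, and Section 12 gives it no hypothesis, sizing or dedicated test. This stands and limits the weight of the point. It does not remove it: the objective is framed by schedule, and positive tests are AESIs, for which Section 12.2 plans comparisons between arms.

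**A matter for the statistical analysis plan.** Anti-N is already a secondary outcome, and a derived seroconversion variable could be defined in the unseen plan. That is possible. However, the protocol itself names the outcome measure for this objective, so the criticism is of a stated choice and not of an absent detail.

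**Infections after day 28.** A reader might infer from Section 13.2 that later infections are not collected, because e-diary entry runs "for a maximum of 28 days following administration of the IMP". The documents do not support this. That sentence governs adverse event data, Sections 7.4 and 9.6.1.1.5 have the diary log infections, and AESIs are asked about at every visit. What remains is that Appendix A shows no diary review after D28 post boost, so the later route could be clearer.

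**Serology as the main outcome.** A reader might want seroconversion to replace self-report. Restricting to seronegative participants would drop those already infected, whom the protocol deliberately enrols and describes as numerous. Selecting on anti-N status at D132 would also condition on a post-randomisation result. Both objections hold, so serology belongs beside self-report.

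**Conclusion.** The point holds as a cheap improvement to an exploratory objective. The sole named outcome depends on test-seeking and disclosure, participants know their arm for about 88% of nominal post-boost follow-up (81% to 89% over the windows), and a less bias-prone measure already in the sampling plan is not linked to the objective.

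The documents do not show that the arm comparison is biased by any particular amount or in any particular direction; they allow only that it could be. No primary or secondary conclusion is affected.

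The conclusion rests on reading day 84 as the D28 post-boost visit, on both vaccines being spike-only as described, and on anti-N sensitivity after vaccination being similar across arms. The last is an assumption, since the documents give no assay performance. Serology would correct ascertainment only; it would not correct for changes in exposure once participants know their arm.

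**What to change.** - In Section 6 and the synopsis, add anti-N seroconversion by arm as an outcome measure for the infection objective, alongside self-report.
- Define it from D56 to D132 and from D56 to D236 post boost, in participants anti-N negative at D56. For those positive at D56, set a rise criterion or report them separately.
- Report self-reported infection separately before and after the day 84 unblinding, and give a combined outcome (self-report or serology).
- State how infections after D28 post boost are recorded, so that Sections 7.4, 9.6.1.1.5 and 13.2 and Appendix A agree. Reconcile the Section 7.2 durations with the D236 visit.

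The cost is protocol wording, a derived variable and a table, with no additional sample or assay. Three limits should be stated with the results: infection is dated only to an interval, some infections just before D56 may seroconvert afterwards and be counted as post-boost, and assay sensitivity after vaccination is not given.
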